Individual randomized trial with stratification by rhythm and permuted blocks of concealed size (Figure 2). To reduce potential bias due to using quasi-random methods or envelopes,^(98, 99) we will place sequentially numbered identically appearing active and sham RIC packages, which will be stored ready for use in a central location in the ED. When an eligible patient arrives in the ED, the medical assistant involved in their care will retrieve the next package and open it at the patient's bedside.

SETTING

Patients will be enrolled after transportation to Harborview Medical Center, Seattle, WA which annually receives a high-volume (≥ 50) of patients resuscitated from OHCA, is capable of performing PPCI 24 hours per day, seven days per week, and is staffed by investigators with a special interest in cardiac resuscitation.

[figure not shown]
POPULATION

Included will be those with:

- a) Age 18 years or more;
- b) Defibrillation by laypersons or defibrillation and/or chest compressions by EMS providers dispatched to the scene;
- c) Non-traumatic etiology of arrest, defined as without concomitant blunt, penetrating, or burn-related injury, or uncontrolled bleeding or exsanguination;

- d) Spontaneous circulation upon emergency department arrival;
- e) No response to verbal commands; and
- f) Ongoing or planned induced hypothermia.

FIGURE 2: DESIGN

Excluded will be those with:

- a) STEMI indicated on first 12-lead ECG obtained after restoration of circulation, defined as ST-elevation of ≥ 2 mm in two or more contiguous ECG leads;
- b) Written do not attempt resuscitation (DNAR) reported to providers before randomization;
- c) Drowning or hypothermia as cause of arrest;
- d) Known prisoner or pregnant; or
- e) Dialysis fistula in either upper extremity; or
- f) Pre-existing amputation of upper extremity.

STUDY TREATMENTS

Experimental Device

A standard non-invasive blood pressure cuff (e.g., American Diagnostics Corporation, Hauppauge, NY but any one can be used off the shelf) and disposable plastic clamp (e.g., Medline Industries Incorporated, Mundelein, IL) can be used to apply RIC in patients resuscitated from OHCA via three cycles of 5-mins. inflation to 200 mmHg followed by 5-mins. deflation of a blood pressure cuff on a thigh. The cuff occludes the artery; the clamp maintains pressure in the air bladder of the cuff during the inflation periods.

Control Group

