The effectiveness of other components of post-resuscitation care remains unclear because observational studies may overestimate the effects of treatment vs. randomized designs.^(116, 117) Importantly, we will mandate those components of post-resuscitation care likely to be associated with survival benefit and monitor others. Mandated components will include: emergent coronary angiography in patients with VF; timing of prognosis assessment and withdrawal of care; and implantable defibrillator insertion as indicated. Prohibited will be sedation with propofol. Monitored components will include: hemodynamic monitoring and support; seizure prevention and control; insulin therapy and oxygenation.

Intervention Group

The intervention group will have an RIC package opened at the bedside as soon as feasible after ED arrival. This package will be identical in size, weight and appearance as that in the control group, but will contain a manual blood pressure cuff and a clamp. The medical assistant will place the cuff around the left upper arm in the usual manner midway between the shoulder and elbow, inflate the cuff by pumping air from a bulb held in her hand through a tube into the cuff's bladder, then place a clamp on the tube to prevent air from leaking out of the bladder. The left arm is the preferred limb so as to leave the right thigh and wrists available for emergency coronary angiography. The left thigh is an alternative site but application of RIC to the upper extremity may be superior than application to the lower extremity.⁽⁸³⁾ The cuff will be kept inflated for 5 minutes then deflated for 5 minutes by the medical assistant intermittently inflating the cuff and applying the clamp or reversing the procedure. This will be repeated for three cycles (i.e. 35 minutes total—last 5 minutes is deflation). All other resuscitative measures will be the same as the control group.

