Survival to 30 Days After Cardiac Arrest assessed as alive 30 days after the index cardiac arrest as confirmed by a brief telephone interview. Note that some experts suggested that the primary outcome of trials in patients with OHCA should be assessed 90 days after discharge.⁽¹⁴¹⁾ However, we showed that such post-discharge scores were well correlated with assessments before discharge.⁽¹⁴²⁾ As well, post-discharge assessment was susceptible to informative missingness as the characteristics of those who consented for follow up were different from those who did not. Lyden and colleagues made similar observations about short vs. long-term outcomes after stroke.⁽¹⁴³⁾ Importantly, post discharge assessments burden patients and prolong study duration. We will confine post-discharge assessment to a brief telephone interview at 30 days.

Accrual is the proportion of eligible subjects who have the study device applied.

SAFETY OUTCOMES

Expected Adverse Events

Device Failure Malfunctions are unlikely due to the simple construction and durable materials of the devices. However, device failure will be defined as discontinuation of use of the device prior to the end of allocated treatment interval because of mechanical failure as opposed to provider preference.

Related to Device RIC is generally well-tolerated, but several side effects will be monitored. Most important are pain at the site of application, or thrombophlebitis, or infection.

Pain assessed using the Richmond Agitation-Sedation Scale at 30 and 60 minutes after randomization in control and intervention group patients.^(144, 145) No gold standard exists for pain assessment in sedated and ventilated patients.⁽¹⁴⁶⁾

Thrombophlebitis assessed as symptomatic non central nervous system venous or arterial thrombus documented radiographically or ultrasonographically.

Sepsis assessed within one week of index arrest as either i) the presence of microbiologically proven, clinically proven, or suspected infection; or ii) presence of Systemic Inflammatory Response Syndrome (SIRS); and iii) development of at least one organ dysfunction within the preceding 24 hours.⁽¹⁴⁷⁾

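### Neither cuff-pain reading is tied to a cuff inflation, and the scale used measures agitation and sedation, so an absence of recorded pain would be weak safety evidence

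*Protocol*

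**What the plan says.** Under Safety Outcomes, Related to Device, the protocol says of the side effects to be monitored: "Most important are pain at the site of application, or thrombophlebitis, or infection". Pain is then defined by a single measure, applied in both arms: "Pain assessed using the Richmond Agitation-Sedation Scale at 30 and 60 minutes after randomization". The next sentence concedes the difficulty: "No gold standard exists for pain assessment in sedated and ventilated patients". No other pain measure is given, and no reading is placed within an inflation.

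The treatment timetable is under Study Treatments, Intervention Group: "The cuff will be kept inflated for 5 minutes then deflated for 5 minutes by the medical assistant", and then "This will be repeated for three cycles (i.e. 35 minutes total—last 5 minutes is deflation". The package is to be opened at the bedside as early as is practicable after arrival. No interval from randomization to first inflation is stated.

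Inclusion criterion (e) under Population is "No response to verbal commands". Screening and Pretreatment Assessments asks for FOUR and SOFA scores before randomization, but for no score on the agitation-sedation scale.

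Two further places bear on the weight of the point. The Specific Aims and the Safety Population paragraph both give safety as a purpose of the study. The Analyses section says that outcomes are summarized descriptively and that no claims will be drawn from the results.

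**The concern.** The stimulus that may hurt is intermittent: three 5-minute inflations, all over within about half an hour of starting. The two readings are fixed to a different clock. If the clocks do not line up, the scale is read while the cuff is down, and any response confined to inflation is not seen. Reading the control arm at the same times is sensible, but a comparison between arms cannot show an inflation effect that was not observed in either.

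The instrument adds to this. By its name, and by the title of one of the two references cited for it, the scale grades agitation and sedation. It is applied to patients who do not respond to speech at entry, and no pre-treatment value is planned against which to judge a change.

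At stake is how much a clean pain result would say. The protocol wants safety information from this pilot to support later use of the device in the field, and pain heads its list of device effects.

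**Working it through.** **Inputs.** Cycle: 5 minutes inflated, 5 minutes deflated, three cycles, stated total 35 minutes (Study Treatments, Intervention Group). Readings: T = 30 and T = 60 minutes after randomization (Safety Outcomes, Related to Device). Lag d from randomization to the start of treatment: not in the protocol, so treated as an assumption and varied from 0 to 60 minutes.

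**Step 1: the protocol's own duration.** Three cycles × (5 + 5) = 30 minutes, with the last inflation ending at 25. The stated 35 minutes is not reproduced; 5 minutes are unexplained. Two readings are carried forward:

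- A: the first inflation begins at the start, so inflations fall at 0-5, 10-15 and 20-25 minutes.
- B: the spare 5 minutes precede the first inflation, so inflations fall at 5-10, 15-20 and 25-30 minutes.

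**Step 2: cuff state at each reading.** The reading at T meets an inflated cuff when T − d lies inside one of the inflation windows.

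| Reading | Timetable | Lags d (minutes) at which the cuff is inflated |
|---|---|---|
| 30 min | A | 5-10, 15-20, 25-30 |
| 30 min | B | 0-5, 10-15, 20-25 |
| 60 min | A | 35-40, 45-50, 55-60 |
| 60 min | B | 30-35, 40-45, 50-55 |

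Under A, for example, the third inflation gives 20 ≤ 30 − d < 25, that is 5 < d ≤ 10.

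**Step 3: share of patients inflated at 30 minutes**, if lags were spread evenly (an assumption used only to show the range):

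| Lags spread over | Timetable A | Timetable B |
|---|---|---|
| 0-5 min | 0/5 = 0% | 5/5 = 100% |
| 0-10 min | 5/10 = 50% | 5/10 = 50% |
| 0-15 min | 5/15 = 33% | 10/15 = 67% |

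At 60 minutes the share is 0% in all six cells, because no lag of 15 minutes or less reaches an inflation.

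**Step 4: what follows.** The 60-minute reading is in practice a post-treatment reading. The 30-minute reading can catch every patient or none, depending on a lag that is not given and a timetable that does not add up.

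**The case against.** The strongest reply is that the measurement is a disclosed compromise. The protocol cites references for the scale, admits that no gold standard exists in such patients, and uses randomization as a clock because it is common to both arms; controls have no inflation to anchor to. Treatment start and cycle completion are recorded, so cuff state at each reading can largely be reconstructed. Staff report adverse events, charts are reviewed daily, and stopping before three cycles counts as attrition. All of this stands, and it limits the harm. None of it measures pain during an inflation.

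A reader might go further than the protocol allows in four ways:

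- **That the cuff is normally deflated at both readings.** At 30 minutes this needs timetable A and a start within 5 minutes. Retrieving and opening the package at the bedside suggests a short lag, but the protocol states none, and under timetable B the same short lag puts the reading inside an inflation.
- **That a null pain result is close to guaranteed.** This assumes that pain shows only while the cuff is inflated, which the protocol does not say. The entry criterion is no response to verbal commands, not to all stimuli, and depth of coma is listed as a covariate.
- **That a null result would be reported as proof of good tolerance.** The Analyses section rules out claims, and the remark that the treatment is generally well tolerated is background.
- **That pain is the main device effect.** It is one of three named together; thrombophlebitis and sepsis have their own definitions.

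**Conclusion.** The point holds as a weakness in one safety measurement. No reading is tied to an inflation. The 30-minute reading falls on a deflated cuff for a lag under 5 minutes and inside the third inflation for a lag of 5-10 minutes, if inflations begin at once; the pattern reverses if the series opens with 5 minutes of deflation. The 60-minute reading misses every inflation unless the start is delayed by at least 30 minutes (timetable B) or 35 minutes (timetable A). Because the scale grades agitation and sedation, an absence of recorded pain would be weak evidence of safety.

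The result rests on the stated 5-minute inflations and on an assumed range for the lag. It does not show that pain will be missed, only that seeing it is left to chance. Attrition as the primary outcome and the sample of 30 are untouched. Separately, the 35-minute total and the 30 minutes implied by the cycles contradict each other and must be reconciled.

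**What to change.** Take the first reading during a cuff inflation, and read controls at a matched time after package opening. Keep the 60-minute reading as the post-treatment value. Report the result as an agitation/sedation response, not as presence or absence of pain. A pre-inflation score would help interpretation but is optional, and should be taken only if it does not delay the start of treatment. Reconcile the stated total duration with the cycle times, since the matched control time depends on the timetable.

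The cost is small: same scale, same staff, same number of planned readings, no change to treatment. The downside is that a control time must be set and the reading coordinated with the cuff cycle in a busy emergency department.

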The null hypothesis is that the attrition rate will be not more than 25%. We assume 59 patients annually are treated by EMS providers for OHCA (21 due to ventricular fibrillation) and have spontaneous circulation upon arrival at the participating receiving hospital. Enrollment of 30 patients (15 per group) will allow estimation of attrition with precision (as measured by half-width of 95% CI) of at least 16.8% overall (and 23.7% within each group).

BACKGROUND AND SIGNIFICANCE

BURDEN

Out-of-hospital cardiac arrest (OHCA) is common, lethal and debilitating. Cardiac arrest has multiple etiologies,

and presumptions about the etiology of arrest influence treatment decisions. Sometimes an identifiable precipitating cause is evident (e.g. traumatic injury, drowning, strangulation, or overdose). In these cases, treatment is directed not only to restoration of circulation, but also to addressing the underlying medical conditions. The majority of OHCA without obvious physical cause is secondary to acute coronary occlusion. In all cases, treatment is directed toward timely restoration of blood flow to the heart and brain.

Extrapolation from observational data reported to the Resuscitation Outcomes Consortium (ROC), suggests that about 424,000 calls to 911 are made annually for individuals who are presumed to have had a non-traumatic OHCA in the United States.⁽⁴⁾ Many of these patients are in such serious condition upon EMS arrival that no attempts at resuscitation are made. Outcome is generally poor among all patients with OHCA treated by EMS; only about 55% of treated cardiac arrest patients having a perfusing rhythm upon transport to an ED, with only 10% of those treated surviving to discharge.

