Collectively, the prior trials demonstrate the efficacy of RIC on an upper extremity for reducing myocardial infarction. The RIC stimulus varied with respect to the number of cycles used, as well as the remote location used. Concurrent medications including intravenous propofol⁽³⁹⁾ may have attenuated the cardioprotective effect of RIC. Although a mortality benefit was not observed, a minority of patients included in the meta-analysis had a large risk for RI as only 429 (23% of enrolled) patients had acute infarction, and the low risk of mortality in patients undergoing elective CABG, elective PCI or other surgical procedures in the meta-analysis limited detection of a mortality benefit with RIC. No patients with cardiac arrest were enrolled.

SAFETY

Application of medical devices (e.g. BP cuff) to the skin may be associated with adverse local effects such as pain or thrombophlebitis. Importantly, RIC is posited to modify the innate immune system, and so could contribute to infection or mask its diagnosis although no signal has been detected in the clinical trials of RIC. The safety of concurrent use of the autoRIC device in humans who may require defibrillation has not been evaluated.

RATIONALE FOR CURRENT PILOT STUDY

Both OHCA and STEMI share elements of RI with inflammatory changes that contribute to myocardial dysfunction and death,⁽⁹⁴⁾ and RIC may be beneficial in both indications: controlled studies in animal models as well as randomized trials in humans suggest that RIC attenuates RI and reduces infarct size in acute myocardial infarction, and controlled studies in animals suggest that RIC may be beneficial in cardiac arrest.

An automated device has been developed and can easily be applied to patients with OHCA to initiate RIC in the post-resuscitation period. However, the Food and Drug Administration (FDA) has not approved any device for RIC due to the absence of any controlled data demonstrating the benefit of RIC in humans with cardiac arrest. Our Institutional Review Board (IRB) has advised us that demonstration of the feasibility of randomization in the emergency department (ED) setting is necessary before proceeding to an assessment of its effectiveness in the out-of-hospital setting.

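### Thrombophlebitis is described as a local cuff effect but defined, as a device event, as any symptomatic imaged non-CNS thrombus with no limb and no onset condition

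*Protocol*

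**What the plan says.** The Safety section of the protocol's background gives the harm as a local one: "Application of medical devices (e.g. BP cuff) to the skin may be associated with adverse local effects such as pain or thrombophlebitis". Under Safety Outcomes, Expected Adverse Events, the entry for events related to the device says "Most important are pain at the site of application, or thrombophlebitis, or infection". The definition follows in the same place: "Thrombophlebitis assessed as symptomatic non central nervous system venous or arterial thrombus documented radiographically or ultrasonographically". The only site it leaves out is the central nervous system. It does not require the thrombus to lie in the cuffed limb, to arise after randomization, or to be judged related to the cuff.

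Three other parts of the protocol bear on how this definition will work:

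- **Cause of arrest.** The Burden section states: "The majority of OHCA without obvious physical cause is secondary to acute coronary occlusion". It adds that acute occlusion is most common when the first recorded rhythm is ventricular fibrillation (VF).
- **Imaging.** The Control Group section under Study Treatments states: "Mandated components will include: emergent coronary angiography in patients with VF". The Intervention Group section applies the same standard care.
- **Cuff site.** The Intervention Group section states: "The medical assistant will place the cuff around the left upper arm in the usual manner", with the left thigh as an alternative. The Experimental Device section speaks only of a thigh.

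**The concern.** The concept and the definition do not match. The concept is injury where the cuff sits. The definition takes in thrombus almost anywhere in the body and at any time, in patients whose arrest was often caused by a thrombus. In VF patients the care plan also requires the imaging that would document it. A culprit coronary thrombus seen at angiography meets the wording although it was present before randomization and lies outside the cuffed limb. A pulmonary embolus that caused the arrest meets it too. In the other direction, phlebitis that is clinically evident in the cuffed limb but never imaged does not meet it.

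This is one of the few device harms the protocol singles out, and the study is meant to confirm that the device is safe for use in the field. In a report that is descriptive only, the definition decides what the safety table shows. A count that mixes arrest-causing thrombi with cuff injuries is hard for the data safety monitoring board or a reader to interpret.

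**Working it through.** The protocol states no expected thrombus rate, so there is no figure of its own to reproduce. The main check is a comparison of sections. The arithmetic only gives scale.

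**1. Does anything in the text keep a pre-existing thrombus out of the device event?**

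- *Limb or onset:* neither is stated. Neighbouring entries do carry a time anchor: pain is assessed 30 and 60 minutes after randomization, and sepsis within one week of the arrest.
- *STEMI exclusion:* the Population section excludes patients with STEMI on the first ECG after circulation returns. The STEMI entry under Secondary and Exploratory Outcomes calls that ECG a poor predictor of acute infarction in these patients, so the exclusion does not reliably remove coronary thrombus.
- *Arrest-related list:* the list of events related to cardiac arrest contains stroke, cerebral bleeding, rearrest and others. It contains no coronary, pulmonary or other non-CNS thrombus, so nothing is diverted there.

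Nothing in the text keeps it out.

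**2. In which arm do such thrombi fall?** The Safety Population is all randomized patients, analyzed by assigned arm, and controls receive a sham package. A thrombus present before randomization is equally likely in either arm. The effect is noise, not directional bias.

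**3. How much noise could there be?**

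From the Sample Size section: 59 eligible arrivals a year, 21 of them VF; 30 patients enrolled, 15 per group.

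- VF share: 21/59 = 0.356. Expected VF patients: 0.356 × 30 = 10.7, taken as 11, or 5 and 6 by arm.
- Assumption: a proportion b of these VF patients shows coronary thrombus at angiography.
- Expected events = 11 × b. P(at least one) = 1 − (1 − b)^11. P(arms differ by two or more) is summed over two independent binomials with n = 5 and n = 6 and the same b.

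| b (assumed) | Expected events | P(at least one) | P(arms differ by ≥ 2) |
|---|---|---|---|
| 10% | 1.1 | 0.69 | 0.12 |
| 20% | 2.2 | 0.91 | 0.25 |
| 30% | 3.3 | 0.98 | 0.33 |
| 40% | 4.4 | 0.996 | 0.37 |

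For comparison, assume a true cuff injury rate of 2% or 7%. The active arm would then gain 15 × 0.02 = 0.3 or 15 × 0.07 = 1.05 events. A chance difference of two events between arms would be larger than either.

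**4. With the narrower definition.** If only new events in the cuffed limb counted and their background rate were near zero, the expected counts would be about 0 in controls and 0.3 or 1.05 in the active arm under the same assumed rates.

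**The case against.** The strongest reply is that the context supplies the limit. The definition sits among side effects of a device, and a clot that was there before the device was applied is not a side effect of it. Coronary events also have their own outcomes (STEMI within 48 h and peak troponin), and sensible staff would not record the cause of the arrest as thrombophlebitis. That may well be what happens. But the protocol writes no such limit for this event, and the separate coronary outcomes do not remove a thrombus from the device count. Classification would rest with whoever abstracts the record.

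Several stronger readings are tempting and are not supported:

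- *That the definition counts systematically against the cuff.* It does not. Events are tabulated by arm against a sham control.
- *That the item mostly measures the cause of the arrest, or cannot show a cuff injury at all.* This is not shown. It would need a thrombus rate and a cuff injury rate, and the protocol gives neither.
- *That the word symptomatic hides limb events because patients are unresponsive.* This cannot be held alongside counting coronary thrombi in the same patients as symptomatic. Unresponsiveness is also required only at enrollment. What stands is narrower: phlebitis without imaging is not counted.

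Broad capture is also defensible in itself, because the protocol says no earlier trial has tested conditioning in cardiac arrest. That part stands and shapes the fix. An embolus arising from the cuffed limb must not disappear into the arrest-related list, whose events are not classified as serious adverse events.

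Finally, the stakes are limited. This is one safety item in a 30-patient pilot whose results are descriptive, and no claims are to be made from them.

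**Conclusion.** The point holds as a mismatch between the stated concept and the working definition. The text lets thrombi that preceded randomization count as device events, and nothing elsewhere in the protocol diverts them. The consequence is noise and chance imbalance between two arms of 15, enough to hide or mimic a cuff signal. It is not a bias in one direction.

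The size is uncertain. The 1 to 4 events rest on an assumed coronary thrombus rate of 10% to 40% and on a VF share taken from all arrivals with spontaneous circulation. Excluding first-ECG STEMI could lower both the VF share and the thrombus rate. Pulmonary emboli, and coronary thrombi in patients without VF, would add to the count. The assumed cuff injury rates of 2% and 7% serve only for comparison. The textual finding depends on none of these figures.

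**What to change.** Reconcile the background Safety section with the definition under Safety Outcomes:

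- **Device event:** new imaging-confirmed venous or arterial thrombus, or clinically documented phlebitis, in the cuffed limb, with onset after randomization. In controls, use the corresponding limb.
- **Record** the site and onset date of each event. Because the protocol names both an arm and a thigh as cuff sites, the limb used must be recorded for every patient in the intervention group.
- **Other new thrombi** after randomization, including pulmonary embolism: tabulate by site and by arm as a separate safety line. Do not move them to the arrest-related list.
- **Thrombi judged present before randomization:** do not count them as device events.

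The cost is a rewritten definition and one extra case report form item. No added imaging is needed. Fewer device events will be counted, and someone must judge whether a thrombus preceded randomization. The separate line keeps the other new thrombi in view. The primary attrition outcome is unaffected.
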